### 6.2.2.2. Analyses Methods

The MCS data will be analyzed descriptively as actual (observed) values and changes from baseline.

An ANCOVA will be used on the MCS change from baseline to compare treatment groups, with treatment as a fixed effect and the baseline MCS as a continuous covariate. Missing data will be imputed using Rubin's multiple imputation (Rubin, 1987). A multivariate normal model will be used as the imputation model. The Markov chain Monte Carlo (MCMC) method will be used to sample from the posterior distribution of the model parameters. The following variables will be used to impute missing data at week 6: MCS baseline value and [REDACTED] at baseline, week 2, 4 and week 6. The imputation model will be separately fitted for each treatment arm. In case the covariance matrix is singular, the imputation method will be changed as follows. The following variables will be used to impute missing data at week 6: MCS baseline value and [REDACTED] at baseline, week 2, 4 and week 6 and treatment arm. The imputation model will no longer be fitted separate for each treatment arm. If the imputation is still problematic after that, then treatment will not be used as a variable for imputation and imputation will not be done separately per treatment arm.

For each imputed dataset, the above ANCOVA model will be used to derive the least squares estimate and standard error of the treatment difference in mean change, and the LS means and standard error for the mean change within each treatment group. Then, these results will be combined using Rubin's rules (Rubin, 1987) to obtain the global least squares estimate and standard error of the treatment difference in mean change, its associated two-sided 90% confidence intervals and p-values for treatment group comparison. The global LS means and standard error and their associate two-sided 90% CIs for the mean change within each treatment group will be also obtained. Further details are provided in Appendix VIII with the SAS code.

The number of patients in the analysis population and number of patients in the analysis will be provided by treatment group.

Listings will be provided for MCS.

#### Sensitivity Analysis 1

As a sensitivity, the above analysis will be performed only allowing data points taken no more than 2 days after day of last dose.

#### Sensitivity Analysis 2

As sensitivity analysis the observed case analysis will be performed by using the same ANCOVA on the MCS change from baseline, with treatment as a fixed effect and the baseline MCS as a continuous covariate. The model will be used to derive least squares estimates of the treatment differences in mean change and two-sided 90% confidence intervals. Also, t-statistics corresponding to the type III sums of squares for the differences in the least squares means will be used to obtain p-values for treatment group comparisons. The LS means and associated two-sided 90% CIs for the mean change within each treatment group will be calculated. The p-values

for the effects will also be presented. The number of patients in the analysis population and number of patients in the analysis will be provided by treatment group.

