## 2.6. Sample Size Justification

A sufficient number of subjects with UC will be screened in order to have 30 subjects randomized (20 planned subjects on GLPG3970 and 10 planned subjects on placebo).

The 30 subjects randomized in the study, are expected to be sufficient to provide preliminary insight in the safety, tolerability and PK of GLPG3970 in UC patients. In case of drop-outs due to SARS-CoV-2 infection, additional subjects may be randomized on top of the planned sample size. The number of additional subjects randomized will not exceed the number of subjects dropping out of the study in relation to SARS-CoV-2. Randomization of additional subjects will ultimately be decided by the sponsor before any study lock or related unblinding has occurred.

For the efficacy objective, the operating characteristics of the chosen decision framework for the most important endpoint (MCS change from baseline at Week 6) at a sample size of 30 subjects (10 on placebo and 20 on GLPG3970) are represented in the following graph and table, and were deemed acceptable. A common standard deviation of 3.3 was assumed in this small study. Lower Reference Value and Target Value for the decision framework were determined based on the published studies and the therapies in development or on the market. They were identified by the project team as the lowest delta of possible interest and the best case scenario for efficacy outcome respectively.

True Treatment Difference In MCS Change From Baseline At Week 6	Signal Score	Probability Of Outcome
-3.0	Signal detected	0.673
	No conclusion	0.220
	No signal detected	0.107
-1.3	Signal detected	0.205
	No conclusion	0.289
	No signal detected	0.506

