### 3. STUDY ESTIMANDS

Estimand for the primary study objective:

Attribute	Details
Treatments	GLPG3970 (400 mg q.d.) vs. Placebo
Population	

Population target defined through the inclusion/exclusion criteria (see CSP).

Analysis Set: Full Analysis Set (FAS) defined as all randomized subjects who have received at least 1 dose of IP.

Endpoint	Change from baseline in total MCS at Week 6.
Population-level summary	Difference (GLPG3970 minus placebo) in least square means (LSM). For further details see study SAP section 6.2.2.2 .
Intercurrent events and strategies to handle those	

Early treatment discontinuation (for any reason) is handled using the hypothetical strategy

Other intercurrent events (e.g. major protocol violations, intake of prohibited medication, lack of compliance) are handled using the treatment policy strategy (i.e. they are ignored)

Estimand for the secondary study objective:

Attribute	Details
Treatments	GLPG3970 (400 mg q.d.) vs. Placebo
Population	

Population target defined through the inclusion/exclusion criteria (see CSP).

Analysis Set: Safety Analysis Set, defined as all subjects who were administered study drug at least once.

Endpoint	Presence of TEAE
Population-level summary	Percentage of subjects with TEAEs.
Intercurrent events and strategies to handle these	

Early treatment discontinuation (for any reason): handled using the while-on-treatment strategy.

Other intercurrent events (e.g. major protocol deviations, intake of prohibited/rescue medication, lack of compliance): handled using the treatment policy strategy (i.e. adverse events are counted regardless the occurrence of these other events).

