**Table 3: Analysis visit window for non-PK data**

Visit date and time	Relative day (ADY)	Assessment visit (VISIT)	Time window (in ADY)*	Target day	Analysis visit (AVISIT)
On or before first study drug administration	$\leq 1$	Last assessment at any point in time before first study drug administration	$\leq 1$	1	Baseline
After first study drug administration	>1	Any scheduled (non follow-up), unscheduled, or early discontinuation visit	2 to 12	8	Week 1
			13 to 22	15	Week 2
			23 to 36	29	Week 4
			37 to 49*	43	Week 6
		Follow-up	CRF collected follow-up visit		Follow-up

\*For Week 1, Week 2, Week 3, Week 4, Week 5 and Week 6, time windows will be applied excluding assessments performed more than 2 days after the last dose of IP. Except for Endoscopy and [REDACTED] where assessments performed more than 7 days after last dose will be excluded and the Week 6 analysis window will be 37 to 52 days.

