#### 6.2.2.1. Derivation Rules

The MCS will be calculated based on the following formula:

$$\text{MCS} = \text{MCS-SF} + \text{MCS-RB} + \text{MCS-ES} + \text{PGA}$$

If one of the component is missing at a specific analysis window, total score will not be calculated for that analysis visit and will be set to missing.

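### The last imputation fallback for Week 6 MCS drops treatment: with collinear scores it still fails, and if it does run it shrinks a real difference (low priority, cheap to change)

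*SAP*

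**What the plan says.** The primary analysis (SAP 6.2.2.2) reads "An ANCOVA will be used on the MCS change from baseline to compare treatment groups, with treatment as a fixed effect", with baseline MCS as covariate. Missing Week 6 MCS is multiply imputed from a multivariate normal model that uses baseline MCS and a redacted auxiliary score at baseline and Weeks 2, 4 and 6. There are three steps:

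- Step 1: a separate imputation model for each arm.
- Step 2: "In case the covariance matrix is singular, the imputation method will be changed as follows". The arms are pooled and treatment arm becomes an imputation variable.
- Step 3: "If the imputation is still problematic after that, then treatment will not be used as a variable for imputation". The arms stay pooled.

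No step reduces the auxiliary scores, and the readable text does not define what counts as problematic. Code and details are deferred to Appendix VIII, which is not readable here.

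Other sections decide who is imputed. SAP section 3: "Early treatment discontinuation (for any reason) is handled using the hypothetical strategy". SAP Table 3, for endoscopy: "assessments performed more than 7 days after last dose will be excluded and the Week 6 analysis window will be 37 to 52 days"; most other assessments are cut off 2 days after the last dose. SAP 6.2.2.1, when one component is missing: "total score will not be calculated for that analysis visit and will be set to missing". Protocol 9.3.4.1 expects some dropout and gives no rate.

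Sensitivity Analysis 1 repeats the imputation with a stricter data cut-off. Sensitivity Analysis 2 does not impute: "As sensitivity analysis the observed case analysis will be performed by using the same ANCOVA on the MCS change from baseline".

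**The concern.** An imputation model should contain the effect that the analysis model estimates. Step 3 leaves it out: missing values in both arms are drawn from one model that does not know the arm, except through whatever part of the effect the earlier scores already carry. Averaging such values into each arm pulls the two means together.

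There is a second weakness. The failure that the SAP names is a singular covariance matrix, and removing treatment does not address the most natural cause of one, which is collinear repeated scores. The trial could then have no working primary imputation. At stake are the primary estimate, its 90% interval and its p-value.

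**Working it through.** **1. Design figures.** "A common standard deviation of 3.3 was assumed in this small study" (SAP 2.6), with 10 placebo and 20 active subjects. SE = 3.3 × √(1/10 + 1/20) = 1.278. With the SAP 6.2.2.3 settings (target −3.0, lower reference −1.3, false stop 10%, false go 20%):

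- signal if the estimate is below −1.3 − 0.842 × 1.278 = −2.376;
- no signal if it is at or above −3.0 + 1.282 × 1.278 = −1.362.

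Probabilities of signal / no conclusion / no signal are 0.687 / 0.213 / 0.100 at a true −3.0 (SAP: 0.673 / 0.220 / 0.107) and 0.200 / 0.281 / 0.519 at −1.3 (SAP: 0.205 / 0.289 / 0.506). All six agree within 0.02.

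**2. Who is imputed.** The Week 6 window opens on Day 37. A last dose before Day 37 − 7 = Day 30 leaves no usable Week 6 endoscopy. Under the 2-day rule, a last dose before Day 37 − 2 = Day 35 leaves no usable Week 6 PGA (unless PGA is the redacted item that shares the 7-day rule). Either gap makes total MCS missing.

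**3. If the scores are collinear.** Some combination of the scores then has zero variance, and treatment has no part in it. Deleting treatment leaves that combination in place, so the matrix stays singular.

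Example, assuming the redacted score is SF + RB + PGA: if all subjects share one baseline MCS-ES value, baseline MCS equals the baseline auxiliary score plus a constant. In 120,000 simulated complete 30-subject trials (40,000 for each assumed share of 70%, 80% and 90% with one value), the pooled model with treatment was singular in 2, 45 and 1,715 trials, that is 0.005%, 0.11% and 4.3%. As a check, 0.9^30 + 0.1^30 = 4.2%. Removing treatment cured 0 of the 1,762. Removing the baseline auxiliary score and keeping treatment cured all 1,762. The same algebra holds at Week 6: if all observed Week 6 MCS-ES values are equal, the model stays singular until the Week 6 auxiliary score is removed.

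**4. If step 3 runs: limit with baseline data only.** Let m be the missing fraction in an arm and w its share of the observed subjects. Set the placebo mean to 0 and the active mean to δ. Every imputed value then has mean w_active × δ, and the expected difference is δ × (1 − m_active × w_placebo − m_placebo × w_active).

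- 20% missing in both arms (8 and 16 observed): 0.2 × 1/3 + 0.2 × 2/3 = 20% shrinkage, equal to the missing fraction.
- 30% placebo, 10% active (7 and 18 observed): 0.1 × 0.28 + 0.3 × 0.72 = 24.4%.

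**5. If step 3 runs: with Week 2 and Week 4 scores.** Simulation of 4,000 trials per cell, true difference −3.0, random dropout, half after Week 2 and half after Week 4. Two correlation structures were assumed. Week 4 to Week 6 correlation is 0.80 (A) or 0.55 (B). The share of the MCS effect visible on the auxiliary score at Weeks 2 / 4 / 6 is 0.37 / 0.60 / 0.75 (A) or 0.20 / 0.43 / 0.75 (B). Mean estimates:

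| Dropout per arm | A: step 3 v step 2 | B: step 3 v step 2 | Shrinkage A / B |
|---|---|---|---|
| 10% | −2.86 v −3.02 | −2.74 v −2.98 | 5% / 8% |
| 20% | −2.64 v −2.96 | −2.48 v −2.96 | 11% / 16% |
| 30% | −2.55 v −3.03 | −2.25 v −2.97 | 16% / 24% |

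A separate large-sample run at 20% dropout, under three other assumed patterns, gave −2.74 (early effect), −2.62 (moderate) and −2.44 (weak auxiliary scores), a loss of 8%, 12% and 18%. Keeping treatment gave −2.98 to −2.99.

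At 20% dropout the loss under A and B is 0.32 and 0.48 points, or 0.32/1.278 = 0.25 and 0.48/1.278 = 0.38 of the design SE. With a true difference of 0, both steps average within 0.04 of zero. If only endoscopy is missing in 20%, shrinkage is 2–3%.

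**The case against.** The strongest reply is that no one has shown the biased path in operation. Step 3 gives an estimate only if step 2 fails and step 3 then succeeds. Under exact collinearity step 3 fails as well. In nearly collinear simulated trials step 2 still returned estimates, so the SAP would not have moved on. What remains is some other convergence problem, with no example and no frequency. This stands. A reader might infer from the table that the primary estimate is biased, or is likely to be; the documents do not support that. The shrinkage figures are conditional on an event that is probably very rare.

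Other points stand in part. The bias is toward no effect and vanishes when there is none. Sensitivity Analysis 2 would expose it, averaging −2.96 (A) and −2.97 (B) at 20% random dropout. It is not the primary analysis, however, and Sensitivity Analysis 1 reruns the same imputation. Appendix VIII may contain settings that make any fallback unnecessary.

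A reader might also infer that keeping treatment removes bias altogether. It does not when dropout depends on scores that have been taken out of the model; the figures are given with the cost of the change. Nor has the replacement been tested in a case where treatment itself causes the failure.

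**Conclusion.** The point holds as a low-priority flaw in a contingency rule. The better demonstrated defect is that, with collinear scores, step 3 cannot repair the imputation, and the readable SAP offers nothing after it. The conditional defect is attenuation: roughly 8–18% of a true difference at 20% dropout, up to the missing fraction when dropout is equal in both arms and leaves only baseline data (24.4% in the unequal example), and none under no effect.

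These sizes rest on assumed dropout rates, correlations and time course of effect. The singularity frequencies also rest on an assumed identity for the redacted score. The case for changing the text is that a pre-specified last step should be sound and that the change is cheap, not that the step is likely to be used.

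**What to change.** Leave steps 1 and 2 unchanged and replace the last fallback in SAP 6.2.2.2 with:

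*If the pooled imputation still fails, treatment arm stays in the imputation model and the auxiliary score is removed one time point at a time (baseline, then Week 2, then Week 4, then Week 6) until the model runs; the final model contains baseline MCS, Week 6 MCS and treatment arm only.*

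The Week 6 removal is needed as the end point, for the reason shown in item 3 of the working.

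The cost is one sentence and a few lines of code, ideally before database lock and unblinding. Precision hardly changes. At 20% random dropout the median 90% CI half-width (A / B) is 2.41 / 2.47 for full step 2, 2.41 / 2.46 without the baseline auxiliary score, 2.44 / 2.47 also without Week 2, and 2.50 / 2.48 also without Week 4.

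The real cost arises when dropout depends on the removed scores. With worse scores making dropout likelier (25% placebo, 14% / 18% active, true −3.0), the first three removals average −2.98 / −3.00, −2.90 / −2.98 and −2.76 / −2.89. Step 2 gives −2.98 / −3.01, observed cases −2.76 / −2.89, and the current step 3 −2.63 / −2.42. The fourth removal was not simulated. For dropouts without a Week 6 auxiliary score it should behave much like the third; where only endoscopy is missing it gives up useful information.

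If the analysis has already been run, stating which imputation step was used settles whether the point has any effect.

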## 2.3. Study Design

This is a Phase 2, randomized, double-blind, placebo-controlled, multi-center parallel-group study to evaluating GLPG3970 in adult subjects with moderately to severely active UC. In this study, subjects will receive 1 dose level of GLPG3970 (400 mg once daily [q.d.]).

The study is planned to randomize 30 subjects in a 2:1 ratio (20 subjects planned to receive GLPG3970 and 10 subjects planned to receive placebo).

The study will consist of 3 study periods:

[figure not shown]
- Screening period: up to 5 weeks with 2 study visits, with a maximum of 2 weeks from screening visit 2 until randomization.
- Double-blind treatment period: 6 weeks with 4 study site visits (Days 1, 15, 29, and 43 or early discontinuation [ED]) and 1 telephone call (Day 8).
- Follow-up period: 2 weeks with 1 study visit.

The subjects will be in the study for a duration of a maximum of 13 weeks [screening to follow-up (FU)] and will receive oral GLPG3970 or placebo, as a reconstituted oral solution, once daily (q.d.) for 6 weeks.

Refer to the Schedule of Assessments ([Section 2.5](#)) for further details.

A schematic diagram of clinical study design, procedures and stages is provided in [Figure 1](#).

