### 6.2.1. Level of Significance

Statistical tests for efficacy analysis will be done at a 2-sided significance level of 10%.

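### The primary analysis cites Rubin's 1987 pooling rules without small-sample degrees of freedom; unless Appendix VIII sets them, the 90% interval uses a near-normal quantile with 30 subjects

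*SAP*

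**What the plan says.** SAP 6.2.2.2 (Analyses Methods) analyses change from baseline in total MCS at Week 6 by ANCOVA "with treatment as a fixed effect and the baseline MCS as a continuous covariate". Missing Week 6 values are multiply imputed under a multivariate normal model. The first choice is stated as "The imputation model will be separately fitted for each treatment arm". If the covariance matrix is singular, both arms are imputed together with treatment as a variable; if that also fails, treatment is dropped.

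For the estimates from the imputed datasets, "these results will be combined using Rubin's rules (Rubin, 1987". This yields the pooled treatment difference, its two-sided 90% CI and p-value, and the LS means with their CIs. No degrees of freedom appear in the visible text. The section closes the description with "Further details are provided in Appendix VIII with the SAS code", and that appendix is not visible in the available copy.

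Sensitivity Analysis 2, in the same section, fits the same ANCOVA to observed cases. There, "t-statistics corresponding to the type III sums of squares for the differences in the least squares means will be used to obtain p-values".

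SAP 6.2.1 sets a two-sided 10% level for efficacy. On size, SAP 2.3 says "The study is planned to randomize 30 subjects in a 2:1 ratio", that is 20 on GLPG3970 and 10 on placebo.

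**The concern.** Rubin's 1987 degrees of freedom were derived for large samples. They grow without limit as the missing-data share shrinks, even when the complete-data model has few residual df. Here the ANCOVA has three parameters (intercept, treatment, baseline MCS), so 30 subjects leave 27. When few values are missing, the 1987 rule refers the pooled statistic to what is in effect a normal distribution.

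Two things are at stake. The primary interval can be a little too narrow for a reason unrelated to missing data. The primary analysis and Sensitivity Analysis 2 would also use different reference distributions, so part of any difference between them would come from the df and not from the handling of missing data.

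**Working it through.** **Inputs.** n = 30, split 20:10 (SAP 2.3). Three ANCOVA parameters (SAP 6.2.2.2), so complete-data df = 30 − 3 = 27. Two-sided 10% level (SAP 6.2.1). SD 3.3 (SAP 2.6: "A common standard deviation of 3.3 was assumed in this small study"). The visible text gives neither the number of imputations m nor a missing-data rate. I assume m from 5 to 1000 and λ, the share of the pooled variance due to missing data, from 0 to 0.20.

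**The plan's own figure.** The documents give no width or df for the primary CI. The planning SE can be checked against the decision table in SAP 2.6. SE = 3.3 × √(1/10 + 1/20) = 1.278. With known SD and the rules in SAP 6.2.2.3, no signal means an observed difference ≥ −3.0 + 1.2816 × 1.278 = −1.362. A signal means < −1.3 − 0.8416 × 1.278 = −2.376.

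| True difference | Recomputed: signal / no conclusion / no signal | SAP 2.6 |
|---|---|---|
| −3.0 | 0.687 / 0.213 / 0.100 | 0.673 / 0.220 / 0.107 |
| −1.3 | 0.200 / 0.281 / 0.519 | 0.205 / 0.289 / 0.506 |

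The largest gap is 0.014, so an SE of 1.278 is a fair basis for scale.

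**Complete data.** With λ = 0 the 1987 df are infinite and the 0.95 quantile is 1.645. The ANCOVA's own quantile is t27 = 1.703.
- Width: 1 − 1.645/1.703 = 3.4% narrower.
- Error: P(|t27| > 1.645) = 0.112 instead of 0.10.
- Half-width on the planning SE: 1.645 × 1.278 = 2.10 against 1.703 × 1.278 = 2.18.
- Example: a test statistic of 1.68 gives p = 0.093 under the normal and p = 0.104 under t27, on opposite sides of the 10% level. With complete data the primary analysis and Sensitivity Analysis 2 have the same estimate and SE, so this conflict would arise on identical data.

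**Some data missing.** The 1987 df are νm = (m − 1)/λ². The Barnard-Rubin df are ν = 1/(1/νm + 1/νobs), with νobs = (28/30) × 27 × (1 − λ).

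For m = 20 and λ = 0.10: νm = 19/0.01 = 1900; νobs = 22.68; ν = 22.4. The quantiles are 1.6457 and 1.7158, so the 1987 interval is 4.1% narrower.

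| λ (m = 20) | 1987 df | Barnard-Rubin df | 1987 interval narrower by |
|---|---|---|---|
| near 0 | effectively infinite | 25.2 | 3.7% |
| 0.05 | 7600 | 23.9 | 3.9% |
| 0.10 | 1900 | 22.4 | 4.1% |
| 0.15 | 844 | 20.9 | 4.3% |
| 0.20 | 475 | 19.3 | 4.6% |

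The last column hardly changes with m. At λ = 0.30 it would be about 5.3%.

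**Coverage by simulation.** 3000 trials per row, m = 20, SD of change 3.3, assumed correlation 0.6 between an earlier score and Week 6, Week 6 values missing completely at random. The Monte Carlo standard error is √(0.9 × 0.1/3000) = 0.5 points.

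| Missing | Imputation | 1987 df | Barnard-Rubin df |
|---|---|---|---|
| 0 of 30 | none needed | 88.9% | 90.3% |
| 3 of 30 | pooled, with treatment | 88.9% | 90.3% |
| 5 of 30 | pooled, with treatment | 90.6% | 91.9% |
| 3 of 30 | per arm | 91.2% | 92.3% |
| 5 of 30 | per arm | 93.3% | 94.2% |

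Other simulations under different assumptions agree in direction.
- Complete data: 88.7% with the 1987 rule against 89.9% with the small-sample df.
- Pooled imputation: 89.1% to 89.3% against 90.1% to 90.5% in one set. In another (2000 trials, 30 imputations, 10% to 23% missing), non-coverage was 11.0% to 11.3% against 9.6% to 10.2%.
- Per-arm imputation, 1987 rule: about 90% to 95%.
- A small run of 400 trials (standard error about 1.5 points) gave 90.0% and 89.6% per arm, and 90.8% and 87.0% pooled.

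**The case against.** The strongest reply is that the df are not known. The SAP leaves the implementation to Appendix VIII, and its Version History records that version 3.0 clarified the SAS code there. The 1987 citation may refer only to how estimates and standard errors are combined, and the code may already pass 27 df to the pooling step. This stands, and it makes the point conditional.

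Second, a reader might infer that the primary interval is simply 4% too narrow and anticonservative. The documents do not support that. The first-choice imputation is per arm, and with data missing that method did not fall clearly below 90% in any simulation: noisy draws from about 10 placebo subjects inflate the pooled variance and more than make up for the quantile. Even for pooled imputation, one setting with 5 of 30 missing gave 90.6%. What remains is complete data, and pooled imputation in most but not all settings. Pooling is a specified fallback, and a singular covariance matrix is a real possibility with so few placebo subjects. Over-coverage from noisy imputation is also a separate effect and does not justify a reference distribution that ignores sample size.

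Third, the effect is small: about 0.07 points of half-width on a 0 to 12 scale, in an exploratory study, and Sensitivity Analysis 2 already supplies t-based p-values. This also stands and sets the severity.

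**Conclusion.** The point holds conditionally and at low severity. The text cites a rule whose df ignore the ANCOVA's 27 residual df, and the visible plan adds no correction. If Appendix VIII does not supply the complete-data df:

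- With no missing data, the 90% CI is 3.4% narrower than the ANCOVA's own interval and the error is 11.2%. This is algebra and needs no missing-data assumption.
- For λ from 0 to 0.20 the interval is about 3.7% to 4.6% narrower than with Barnard-Rubin df. That range rests on assumed λ and m.
- Coverage falls short by about 1 point with complete data and, in most simulated settings, with pooled imputation. It does not clearly fall short with per-arm imputation and missing data.

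The point estimate and SE are unaffected. Any effect on the signal-detection output cannot be judged, because SAP 6.2.2.3 leaves its details to a separate document. It would go too far to call the analysis wrong as written, since the operative code is not visible.

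**What to change.** State in SAP 6.2.2.2, and confirm in the Appendix VIII code, that pooled CIs and p-values for the treatment difference and for the LS means use Barnard-Rubin degrees of freedom, with complete-data df equal to the number analysed minus 3 (27 at n = 30). If the code already does this, only the sentence is needed.

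The cost is one sentence and one setting in the pooling step. The CI becomes about 4% wider, and over-coverage grows somewhat if per-arm imputation is used with several missing values (93.3% to 94.2% in the simulated case with 5 of 30 missing). With complete data, agreement with Sensitivity Analysis 2 is close but not exact: Barnard-Rubin gives 25.2 df and a quantile of 1.708, against 1.703 for t27.
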